6.3. Prohibition and Restrictions

6.3.1. Precautions for Sexual Intercourse

Highly effective contraceptive measures for both males and females of childbearing potential must be documented in the source documents.

6.3.1.1. Female Subjects

Female subjects are considered of non-childbearing potential if they meet one of the following criteria:

- No menses for 12 or more months without an alternative medical cause. A high follicle stimulating hormone (FSH) level in the postmenopausal range may be used to confirm a postmenopausal state in women not using hormonal contraception or hormonal replacement therapy. However in the absence of 12 months of amenorrhea, a single FSH measurement is insufficient.
- Permanently surgically sterile (bilateral oophorectomy, i.e. surgical removal of ovaries, bilateral salpingectomy or hysterectomy, i.e. surgical removal of uterus).

All other female subjects are considered to be of childbearing potential (WOCBP) and must use one of the following highly effective methods of birth control prior to the first dose of IP, during the clinical study and for at least 35 days after the last dose of IP:

- Combined (estrogen and progesterone containing) (oral, intravaginal, transdermal) hormonal contraception associated with inhibition of ovulation plus a barrier method.
- Progesterone-only hormonal (oral, injectable, implantable) contraception associated with inhibition of ovulation plus a barrier method.
- Intrauterine device.
- Intrauterine hormone-releasing system plus a barrier method.
- Bilateral tubal occlusion.
- Sexual abstinence defined as refraining from heterosexual intercourse during the entire period of risk associated with the study treatments. The reliability of sexual abstinence needs to be evaluated in relation to the duration of the clinical study and the preferred and usual lifestyle of the subject.

Periodic abstinence (e.g. calendar, symptothermal, post-ovulation methods), declaration of abstinence for the duration of a clinical study, withdrawal, spermicides only, and lactational amenorrhea method are not acceptable as methods of contraception.

In case a WOCBP has a vasectomized partner, provided that partner is the sole sexual partner of the WOCBP clinical study participant and that the vasectomized partner has received medical assessment of the surgical success, then she is not required to use an additional form of contraception.

Within these limits, the specific forms of contraception employed are left to the discretion of the subject, the investigator, and/or the subject's physician.

The safety of GLPG3970 during breastfeeding is unknown. Nursing women are not allowed to take part in this clinical study.

6.3.1.2. Male Subjects

Non-vasectomized male subjects with female partners of childbearing potential must be willing to use a condom from the time of the first dose of IP, during the clinical study and for at least 7 days after the last dose of IP, in addition to having their female partner use one of the following forms of contraception:

- Combined (estrogen and progesterone containing) (oral, intravaginal, transdermal) hormonal contraception associated with inhibition of ovulation.
- Progesterone-only hormonal (oral, injectable, implantable) contraception associated with inhibition of ovulation.
- Intrauterine device.
- Intrauterine hormone-releasing system.

Sexual abstinence defined as refraining from heterosexual intercourse is considered a highly effective contraceptive measure only if it is the preferred and usual lifestyle of the subject. The reliability of sexual abstinence needs to be evaluated in relation to the duration of the clinical study.

Periodic abstinence (e.g. calendar, symptothermal and post-ovulation methods), declaration of abstinence for the duration of a clinical study, withdrawal, spermicides only and lactational amenorrhea method are not acceptable methods of contraception.

In a case where the female partner of a male subject has undergone documented surgical sterilization that was performed more than one year before screening, then the subject is not required to use an additional form of contraception.

Vasectomized male subjects with female partners of childbearing potential are not required to use an additional form of contraception providing that surgical sterilization has been successful (documented azoospermia by semen analysis).

No sperm donation is allowed from the first dose of IP during the clinical study until 7 days after the last dose of IP.

6.3.2. Prior and Concomitant Medications

Prior and concomitant therapies taken for long term treatment of pre-existing conditions are allowed, provided they are in accordance with the inclusion and exclusion criteria (see Section 6.1 and Section 6.2, respectively) and with the prohibitions and restrictions listed below.

Information on previous inadequate response on MTX therapy for RA within 2 years prior to screening should be recorded with approximate dates of use (year, duration in months) and dose.

In case additional concomitant medications need to be administered or dose adjustments for pre-existing conditions (except for RA) are needed during the study, the risk/benefit to the subject should be carefully assessed by the study physician and consideration given to the timing of any necessary introduction of new medications.

If during the study, the subject's condition necessitates the use of prohibited medication, the use of IP may be interrupted, preferably after consultation with the sponsor's medical responsible. Re-introduction of IP can be considered after the treatment course with the prohibited medication has been stopped and after consultation with the sponsor's medical responsible.

During the study, subjects will be instructed to record any change in concomitant medication in a diary (see Section [8.8.1](#)).

Permitted Medications

Permitted medications at screening and during the study include:

- NSAIDs, provided that the dose is stable for at least 2 weeks prior to first IP dosing and, if possible, is kept constant during the study.
- Analgesics, other than NSAIDs, up to the maximum recommended doses may be used for pain as required.
- Oral steroids, provided that the dose is stable, at a dose of ≤ 10 mg/day prednisone or equivalent (see [Appendix 7](#) for prednisolone conversion table) for at least 4 weeks prior to first IP dosing, and is kept stable for the study duration.
- Medications prescribed for the treatment of comorbidities and which are not described as prohibited medications.

Prohibited Medications

Prohibited medications during the study include any DMARDs, other than background MTX, including:

- Oral or injectable gold, sulfasalazine, antimalarials, azathioprine, or D-penicillamine within 4 weeks prior to screening,
- cyclosporine within 8 weeks prior to screening,
- leflunomide within 3 months prior to screening or within 4 weeks prior to screening if after 11 days of standard cholestyramine therapy.

Current or previous treatment with a bDMARD. Except for subjects who received bDMARDs in a single clinical study setting:

- For whom the last dose of bDMARD ≥ 6 months prior to screening (12 months for rituximab or other lymphocyte depleting agents), AND;
- For whom the bDMARD was effective, without being discontinued due to lack of efficacy.

Previous treatment during the year before screening as well as during the study, with a cytotoxic agent other than MTX, is prohibited. These agents include, but are not limited to chlorambucil, cyclophosphamide, nitrogen mustard, and other alkylating agents.

Receipt of an intra-articular or parenteral corticosteroid injection within 4 weeks prior to screening is prohibited.

Other prohibited medications and dietary/herbal products:

The following medications should be discontinued at least 2 weeks or 5 half-lives of the drug, whichever is longer, prior to the first dose of IP administration and throughout the study.

- [REDACTED]
- [REDACTED]
- [REDACTED]
- [REDACTED]
- [REDACTED]

Additional guidance the use of concomitant medications:

- [REDACTED]
- [REDACTED]
- [REDACTED]
- [REDACTED]

— [REDACTED]

■ [REDACTED]

The lists provided in [Appendix 1](#) through [Appendix 6](#) are non-exhaustive. In case of questions on concomitant medications, the sponsor's medical monitor (as per study contact list) and sponsor's medical responsible can be contacted.

6.3.3. Food and Beverage Restrictions

Subjects must come for the study visits, during the treatment and FU period, in the morning. At Visit 1, 3, 5, and if applicable the ED visit, subjects need to come for the study visits in a fasting state (no food intake for at least 8 hours).

Subjects will refrain from the consumption of grapefruit juice, grapefruit or Seville oranges beginning 48 hours prior to administration of the initial dose of IP, throughout the study until 7 days after the last IP administration.

6.4. Treatment Discontinuation (Temporarily and Permanently), Subject Withdrawal and Study Termination

A subject may be withdrawn from the clinical study at any time without the subject's consent if the investigator or sponsor determines that it is not in the best interest of the subject to continue participation. In such case, the reason for withdrawal will be documented in the source

documents, and the subject will be asked to complete the ED visit and FU visit for safety assessments.

Treatment with IP should be discontinued by the investigator (who may consult the sponsor's medical responsible) for any of the following conditions:

- Life-threatening adverse event (AE) or a serious adverse event (SAE) that places the subject at immediate risk.
- Serious infections deemed related to study treatment by the investigator, and requiring parenteral antimicrobial therapy and/or hospitalization.
- Confirmed pregnancy or lactation.
- Arrhythmia or conduction abnormality, including but not limited to prolonged QT interval corrected for the heart rate using Fridericia's formula (QTcF), where the severity is categorized as Common Terminology Criteria for Adverse Events (CTCAE) Grade 3 or higher (QTcF >500 ms on at least 2 separate ECGs) or clinically significant arrhythmia of any grade.
- Liver enzyme increase (see also [Appendix 8](#))
 - AST and/or ALT ≥ 8 x the ULN.
 - AST and/or ALT elevations ≥ 3 x ULN with signs of liver damage (i.e. with the appearance of fatigue, nausea, vomiting, right upper quadrant pain or tenderness, fever, rash and/or eosinophilia [$>5\%$], and/or total bilirubin ≥ 2.0 x ULN or international normalized ration [INR] >1.5)
 - In addition, a dose interruption or reduction (if applicable) should be considered if AST and/or ALT ≥ 3 x ULN and <5 x ULN and dosing with IP should be interrupted if AST and/or ALT ≥ 5 and <8 x ULN.
- Subjects presenting with signs and symptoms of SARS-CoV-2 infection should immediately contact the site investigator, who should inform the sponsor's medical responsible as soon as possible, and report an AE/SAE as applicable. In case of suspected SARS-CoV-2 infection RT-PCR and serology tests should be performed to confirm the infection. The investigator, preferably after consultation with the sponsor's medical responsible, must discontinue the subject from the study. The subject could be tested for SARS-CoV-2 in facilities outside the study site and if so, the subject should be instructed to immediately inform the study investigator if the test is positive and test results should be shared with the investigator as soon as possible.

For subjects having:

- AST or ALT ≥ 8 xULN
- AST or ALT ≥ 3 xULN with signs of liver damage (i.e. with the appearance of fatigue, nausea, vomiting, right upper quadrant pain or tenderness, fever, rash and/or eosinophilia [$>5\%$], and/or total bilirubin ≥ 1.5 xULN or INR >1.5)

The following steps will need to be performed by the investigator:

- The site should immediately contact the subject and require the subject to discontinue IP immediately. The subject should be asked to return to the site within a 48-hour window from awareness of the result.
- A full evaluation of various causes of hepatitis should be conducted (i.e. infectious, alcohol, medications, anatomical).
- An assessment of other concomitant medications and standard of care should be made. The investigator should consider whether it is in the best interest of the subject to stop/interrupt concomitant medications and standard of care treatment.
- A detailed history including relevant information on alcohol use, recreational drug use, supplement consumption, any herbal remedies, family history, sexual history, travel history, history of contact with a jaundiced subject, surgery, occupational history, blood transfusion, history of liver or allergic disease, and any other potential causes of attributable to a liver insult should be collected.
- A detailed assessment of the subject's clinical condition and repeat laboratory tests for liver function tests (LFT), including albumin, creatine kinase, total bilirubin (direct and indirect), gamma-glutamyl transferase (GGT), INR, and alkaline phosphatase should be done.
- Further testing for hepatitis A, B, and C, and for autoimmune hepatitis should be done. Other causes of viral hepatitis (cytomegalovirus or Epstein Barr virus etc) should be excluded. Liver imaging should be considered.
- Referral to a hepatologist or gastroenterologist should be requested.
- All these cases should be reported as SAEs.

If during the study, the subject's condition necessitates the use of prohibited medication, the use of IP may be interrupted, preferably after consultation with the sponsor's medical responsible. Re-introduction of IP can be considered after the treatment course with the prohibited medication has been stopped and after consultation with the sponsor's medical responsible.

Every effort should be made to keep subjects in the study and on treatment. However, the investigator, who may consult the sponsor's medical responsible, can consider stopping the study treatment in case of concerns about the subject's safety, serious or severe AEs or worsening of the disease condition, which in the investigator's opinion needs an alternative treatment approach not being covered in the clinical study (e.g. rescue medication). If IP treatment is interrupted due to an SAE, IP could be restarted, as per the investigator's judgment and after consultation with the sponsor's medical responsible.

When study treatment is discontinued, the subject will be requested to complete the assessments for the ED visit and return for the FU visit. Reason for discontinuation must be documented in the case report form (CRF).

Subjects will be informed prior to clinical study entry that they are allowed to withdraw from the clinical study. At any time and for any reason, a subject's participation in the clinical study may terminate at his/her request without prejudice to his/her future medical care. The subject will be encouraged to share the reason(s) for withdrawal so this can be documented in the source

documents, and to complete the ED visit and FU visit for safety assessments, but will not be obliged to do so.

Subjects who withdraw from the clinical study without contact with the site (lost-to-FU) should be contacted by the site so that their health status can be assessed and documented in the source documents. The site should make every effort to understand whether the subject is alive, including checking the medical records and contacting general practitioner or relatives, if necessary. All attempts must be documented in the source documents.

The sponsor has the right to terminate the clinical study at any time and for any reason. In this event, the investigator(s) and relevant authorities will be informed of the reason for clinical study termination.

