11.1.4. Adverse Events of Special Interest

Not applicable.

11.1.5. Clinical Laboratory Abnormalities and Other Abnormal Assessments as Adverse Events or Serious Adverse Events

Laboratory abnormalities without clinical significance based on the investigator's judgment are not considered AEs or SAEs. However, laboratory abnormalities (e.g. clinical chemistry, hematology, and urinalysis) or other abnormal (clinical study-specific) assessments (e.g. ECG, radiography, vital signs) that require medical or surgical intervention, are associated with signs and/or symptoms, and/or lead to IP interruption, modification or discontinuation must be recorded as an AE or SAE if they meet the definition as described in Sections 11.1.1 and 11.1.2, respectively. If the laboratory abnormality is part of a syndrome, the syndrome or diagnosis is to be reported (e.g. anemia instead of decreased hemoglobin).

The following liver enzyme elevations should be reported as SAEs:

- AST or ALT ≥ 8 xULN.
- AST or ALT ≥ 3 xULN with signs of liver damage (total bilirubin >2 xULN OR international normalized ratio >1.5 , and/or with the appearance of fatigue, nausea, vomiting, right upper quadrant pain or tenderness, fever, rash and/or eosinophilia [$>5\%$]).

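### Protocol Section 6.4 gives two bilirubin limits, 2.0 and 1.5 x ULN, for stopping study drug in the same liver case

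*Protocol*

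**What the plan says.** Four places in the protocol define the bilirubin limit that, together with AST or ALT of at least 3 x ULN, counts as a sign of liver damage.

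- **Section 6.4, conditions for discontinuing IP:** "total bilirubin ≥ 2.0 x ULN or international normalized ration [INR] >1.5". Without liver signs, the same list asks the investigator to consider interruption or reduction at AST/ALT 3 to below 5 x ULN, and to interrupt at 5 to below 8 x ULN.
- **Section 6.4, investigator steps:** "total bilirubin ≥ 1.5 xULN or INR >1.5". The site must "require the subject to discontinue IP immediately" and have the subject return within 48 hours. The steps add "Referral to a hepatologist or gastroenterologist should be requested" and end with "All these cases should be reported as SAEs".
- **Section 11.1.5, liver elevations to report as SAEs:** "total bilirubin >2 xULN OR international normalized ratio >1.5".
- **Appendix 8, footnote 1:** bilirubin at or above 2.0 x ULN. Footnote 3 attaches the same steps and the same SAE sentence as Section 6.4.

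The other liver signs (INR above 1.5, the listed symptoms, eosinophilia above 5%) are the same in all four. No text ranks one place above another.

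**The concern.** Both limits in Section 6.4 govern the same action, stopping IP. A lower limit that triggered only extra work-up could be a deliberate second tier. Here, however, the first step under the 1.5 x ULN limit is immediate discontinuation, so the two lists conflict.

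Two sites could each follow the protocol and treat the same subject differently. One would stop IP at once, request a specialist referral and file an SAE, which Section 11.3.2 makes due within 24 hours. The other would interrupt IP, or only consider doing so. This is a liver rule in the first study of the drug in RA, given on top of methotrexate. SAE status also feeds expedited reporting and the serious-TEAE tables. With 15 and 10 planned subjects, one case classified differently moves a row by 1/15 = 6.7 or 1/10 = 10 percentage points.

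**Working it through.** **Where the rules disagree.** Take a subject with INR at or below 1.5, no listed symptom and no eosinophilia above 5%, so that only bilirubin can supply the liver sign.

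- AST/ALT below 3 x ULN: none of the liver-sign rules applies.
- AST/ALT 8 x ULN or above: every rule says discontinue, and every SAE list includes the case.
- Bilirubin below 1.5 x ULN: neither limit is met.
- Bilirubin 2.0 x ULN or above: both limits in Section 6.4 are met. At exactly 2.0, only Section 11.1.5 (above 2) is not.

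What remains is AST/ALT in [3, 8) x ULN with bilirubin in [1.5, 2.0) x ULN.

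**Two worked cases (multiples of ULN).**

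| Text | ALT 3.5, bilirubin 1.7 | ALT 6, bilirubin 1.7 |
|---|---|---|
| 6.4 discontinuation list | Consider interruption or reduction | Interrupt |
| 6.4 investigator steps | Discontinue at once, SAE | Discontinue at once, SAE |
| Appendix 8 | Reduce or interrupt for at least 2 weeks, close observation; not a listed SAE | Interrupt for at least 2 weeks, close observation; not a listed SAE |
| 11.1.5 | Not a listed SAE | Not a listed SAE |

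The IP conflict lies inside Section 6.4. The SAE mismatch is between the investigator steps in Section 6.4 on one side and Section 11.1.5 and Appendix 8 on the other.

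**Doses at stake.** Section 8.11 schedules on-treatment safety bloods on Days 15, 29 and 43, and IP is taken up to Day 43. Laboratory turnaround is not stated, so assume the result is acted on 1, 2 or 3 days after the draw.

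- Doses left without interruption = 43 − action day + 1.
- Doses left after a 14-day interruption = that number − 14, not below 0.

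| Draw | Action day | No interruption | After 14-day interruption | After discontinuation |
|---|---|---|---|---|
| Day 15 | 16, 17, 18 | 28, 27, 26 | 14, 13, 12 | 0 |
| Day 29 | 30, 31, 32 | 14, 13, 12 | 0, 0, 0 | 0 |
| Day 43 | after last dose | 0 | 0 | 0 |

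The no-interruption column applies only to the discontinuation list at AST/ALT 3 to below 5 x ULN, when the investigator considers interruption and decides against it. The 14-day column is Appendix 8 at its minimum duration, with AST and ALT back below 3 x ULN and IP resumed. The last column assumes no restart. After a Day 43 test, only SAE reporting and work-up differ.

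**The case against.** The strongest counter-argument is that all the texts can be satisfied at once. The discontinuation list does not forbid stopping IP in other cases, and the SAE lists do not exclude further cases. A site that acts and reports at 1.5 x ULN therefore breaches nothing. This is correct, and it is why the stricter rule works as an interim measure. It does not tell a site reading only the 2.0 x ULN list or Appendix 8 that it must do more.

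Subjects in the zone are also not left unprotected, and this stands. Appendix 8 requires IP to be reduced or interrupted, with liver tests 2 to 3 times a week, and stops IP if AST or ALT is still at least 3 x ULN after at least 2 weeks. Under Section 11.1.5, abnormalities that "lead to IP interruption, modification or discontinuation must be recorded as an AE or SAE" if they meet the definition. Investigators may class an event as a medically significant SAE by judgment. Laboratory alerts go out at Grade 3 and above, and a committee reviews unblinded safety data. SAP Section 6.3.2.8 tabulates AST/ALT above 3 x ULN with same-day bilirubin above both 1.5 and 2 x ULN. What can still be lost is immediate discontinuation, SAE classification with its 24-hour report, and the referral request, since Appendix 8 leaves specialist consultation under close observation to the investigator's discretion.

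Two limits on the dose counts also stand. The gap between 26–28 and 12–14 doses comes from the separate difference between considering and requiring interruption, not from the bilirubin limit. It is also arguable that discontinuing means stopping for good, because the liver text uses interrupt and discontinue as different words. The protocol does not settle this: Section 11.2.3 lists both temporary and permanent discontinuation, and Section 6.4 says "If IP treatment is interrupted due to an SAE, IP could be restarted".

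**Conclusion.** The concern holds. Section 6.4 contains two stopping thresholds for the same action, and the protocol does not say which governs. Three of the four places use a cut-off at 2 x ULN, so 1.5 looks like the outlier, but the documents do not confirm that.

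The practical size is small. The zone is narrow and the documents give no rate for it. For a subject who falls in it at Day 15, the bilirubin conflict means none versus 12–14 further doses, assuming action within 1 to 3 days, a 14-day interruption that is then lifted, and no restart after discontinuation. SAE status differs as well. The primary analysis is not affected. This is a drafting inconsistency in a safety rule, and it should be fixed.

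**What to change.** The sponsor should confirm the intended limit and use one value with one inequality sign in both lists of Section 6.4, in Section 11.1.5 and in Appendix 8. There are two options:

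- **At least 2.0 x ULN:** two edits, to the investigator steps in Section 6.4 and to Section 11.1.5.
- **At least 1.5 x ULN:** three edits, to the discontinuation list in Section 6.4, to Section 11.1.5 and to Appendix 8 footnote 1.

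Until the correction is issued, sites should follow the stricter 1.5 x ULN rule with its full set of steps.

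A minor alignment can go in at the same time. For AST/ALT 3 to below 5 x ULN without liver signs, Section 6.4 and Appendix 8 should agree on whether interruption is considered or required. The reduction option should also come out of Appendix 8, because Section 5.1 provides only one dose level.

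The cost is wording only, by amendment or clarification letter, with no added visits or scheduled procedures.
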